6.1.1 Adverse Events List(s)
Adverse Event List(s) for naltrexone

Common (10-33%)	Uncommon (1-10%)	Serious (<1%)
Nausea	Vomiting Anorexia Diarrhea	Elevated liver function tests Suicidal ideation

	Constipation Rash Headache Dizziness Nervousness Insomnia Anxiety Irritability Increased thirst	
--	---	--

6.2 Adverse Event Characteristics

Reporting of adverse events:

All toxicities or adverse events occurring between the start of treatment and 30 days following the end of treatment will be recorded and graded as to severity and relationship to study drug. Any toxicity that is moderate or serious will be immediately reported by phone or email to the PI within 24 hours of discovery. All serious adverse reactions will be reported to the PI who will then notify the IRB.

A **serious adverse reaction** is defined as any of the following: life threatening; permanently disabling; requiring inpatient hospitalization or prolonging or hospitalization; death while on study treatment

A **moderate adverse reaction** is defined as the following: discomfort severe enough to cause interference with usual activities; persistent or requiring treatment

A **mild adverse reaction** is defined as the following: awareness of signs/symptoms, but easily tolerated; are of minor irritant type; causing no loss of time from normal activities; symptoms would not require medication or a medical evaluation; signs/symptoms are transient in nature

Preexisting medical conditions and symptoms related to known underlying diseases will not be recorded as adverse events unless they significantly worsen in severity during the course of the study.

Other than possible drug side effects, participants may also experience inconvenience and/or emotional distress, due to filling out instruments focusing on physical and emotional symptoms.

In case of subject distress, study psychiatrists can be contacted.

- **CTCAE term (AE description) and grade:** The descriptions and grading scales found in the revised NCI Common Terminology Criteria for Adverse Events (CTCAE) version 4.0 will be utilized for AE reporting. All appropriate treatment areas should have access to a copy of the CTCAE version 4.0. A copy of the CTCAE version 4.0 can be downloaded from the CTEP web site http://ctep.cancer.gov/protocolDevelopment/electronic_applications/ctc.htm.
- **For expedited reporting purposes only:**
 - AEs for the agent(s) that are listed above should be reported only if the adverse event

varies in nature, intensity or frequency from the expected toxicity information which is provided.

- Other AEs for the protocol that do not require expedited reporting are outlined in the next section (Expedited Adverse Event Reporting) under the sub-heading of Protocol-Specific Expedited Adverse Event Reporting Exclusions.
- **Attribution** of the AE:
 - Definite – The AE *is clearly related* to the study treatment.
 - Probable – The AE *is likely related* to the study treatment.
 - Possible – The AE *may be related* to the study treatment.
 - Unlikely – The AE *is doubtfully related* to the study treatment.
 - Unrelated – The AE *is clearly NOT related* to the study treatment.

6.3 Expedited Adverse Event Reporting

6.3.1 Investigators **must** report to the Overall PI any serious adverse event (SAE) that occurs after the initial dose of study treatment, during treatment, or within 30 days of the last dose of treatment on the local institutional SAE form.

6.3.2 DF/HCC Expedited Reporting Guidelines

Investigative sites within DF/HCC and DF/PCC will report SAEs directly to the DFCI Office for Human Research Studies (OHRS) per the DFCI IRB reporting policy.

6.3.3 Protocol-Specific Expedited Adverse Event Reporting Exclusions

N/A

6.4 Expedited Reporting to Hospital Risk Management

Participating investigators will report to their local Risk Management office any participant safety reports or sentinel events that require reporting according to institutional policy.

6.5 Routine Adverse Event Reporting

All Adverse Events **must** be reported in routine study data submissions to the Overall PI on the toxicity case report forms. **AEs reported through expedited processes (e.g., reported to the IRB, FDA, etc.) must also be reported in routine study data submissions.**

7. PHARMACEUTICAL INFORMATION

A list of the adverse events and potential risks associated with the investigational agent administered in this study can be found in Section 7.1.

7.1 Naltrexone

7.1.1 Description

Naltrexone (a pure opioid antagonist) is a cyclopropyl derivative of oxymorphone similar in structure to naloxone and nalorphine (a morphine derivative). The chemical name is N-Cyclopropylmethylnoroxymorphone and the formula is $C_{20}H_{23}NO_4$. The molecular weight is 341.40092. The NIM PubChem Compound ID is 5360515. Pharmacokinetic information follows below:

Duration: Oral: 25-50 mg: 24 hours

Absorption: Oral: Almost complete

Distribution: V_d : ~1350 L; widely throughout the body but considerable interindividual variation exists

Metabolism: Extensively metabolized via noncytochrome-mediated dehydrogenase conversion to 6-beta-naltrexol (primary metabolite) and related minor metabolites; glucuronide conjugates are also formed from naltrexone and its metabolites

Oral: Extensive first-pass effect

Protein binding: 21%

Bioavailability: Oral: Variable range (5% to 40%)

Half-life elimination: Oral: 4 hours; 6-beta-naltrexol: 13 hours; I.M.: naltrexone and 6-beta-naltrexol: 5-10 days (dependent upon erosion of polymer)

Time to peak, serum: Oral: ~60 minutes; I.M.: Biphasic: ~2 hours (first peak), ~2-3 days (second peak)

Excretion: Primarily urine (as metabolites and small amounts of unchanged drug)

Despite its hepatic metabolism, naltrexone does not interact with the cytochrome P450 enzyme system.

7.1.2 Form

Naltrexone is available generically from various manufacturers as a scored 50mg tablet (white or yellow in color).

7.1.3 Storage and Stability

Naltrexone hydrochloride tablets will be stored in well-closed containers at 15-30 degrees Celsius.

7.1.4 Compatibility

Not applicable for this study

7.1.5 Handling

No special considerations apply to handling for this study

7.1.6 Availability

The agent is commercially available from various manufacturers and will be purchased by the DFCI and MGH Research Pharmacies. Naltrexone will be purchased and billed to the study via established mechanisms at each site. It will be provided free of charge to participants.

7.1.7 Preparation

The DFCI and MGH Research Pharmacies will each purchase and over-encapsulate study medication and matching placebo per standard operating procedures of each site and provide the study drug supply for patients anticipated to go on the trial at the respective sites.

7.1.8 Administration

Orally dosed, once per day, in the morning with food.

7.1.9 Ordering

The agent will be obtained via commercial sources.

7.1.10 Accountability

As the responsible party designated by the investigator, the DFCI and MGH Research Pharmacies will maintain a careful record of the inventory and disposition of the agent using the NCI Drug Accountability Record Form (DARF) or another comparable drug accountability form. (See the NCI Investigator's Handbook for Procedures for Drug Accountability and Storage.)

7.1.11 Destruction and Return

At the end of the study, unused supplies of naltrexone will be destroyed according to institutional policies. Destruction will be documented according to the Drug Accountability Return Form.

8. BIOMARKER, CORRELATIVE, AND SPECIAL STUDIES

At the blood draw obtained for eligibility determination immediately prior to randomization, whole blood samples will be banked for analysis of OPRM1 (mu opioid receptor) genetic variants, specifically the Asn40Asp missense variant which has a frequency of 0.10-0.15 in Caucasians, 0.21 in Ashkenazi Jews, 0.25-0.45 in East Asians, and 0.14 in Hispanics.³³ The Asn40Asp variant has been shown to bind beta-endorphin approximately three times more tightly than the most common allelic form of the receptor,³⁴ and it has predicted good clinical response to naltrexone in alcohol and opioid dependence.^{33,35,36}

Banked specimens will also be available for future exploratory examination of pro-inflammatory biomarkers such as expression-regulating polymorphisms in pro-inflammatory cytokine genes, which in recent studies have correlated with increased fatigue severity, depressive symptoms and memory complaints.³⁷

Participants may opt out of specimen banking if they wish to do so.

9. STUDY CALENDARS

*Note that study visits in both monitoring and intervention phase can be completed within 7 days of the scheduled date.

**Study measures, type of procedure, and study visit schedule
Monitoring Phase (6-week radiation therapy schedule)**

	Type	Baseline Visit	Weekly Monitoring Visits from Start of Radiation Therapy	Meets Fatigue Eligibility Threshold
Background Information Consent Demographics/Patient Characteristics Form Clinical Variables ^a	Self-report	X X	X ^a	
Fatigue FACIT-Fatigue Subscale PGI-F	Self-report Self-report	X ^b X ^b	X	X
Sleep PSQI ISI ESS Berlin Questionnaire	Self-report Self-report Self-report Self-report	X ^b X ^b X ^b X ^b		
Other Target Symptoms GAD7 PHQ9 FACT-B/FACT-ES CPFQ PEG	Self-report Self-report Self-report Self-report Self-report	X ^b X ^b X ^b X ^b X ^b	X ^c X ^c	
Safety monitoring Urine β -HCG LFTs ^d BUN/Creatinine ^d Hematocrit ^d TSH ^d				X X X X X
Subject Exit form (if applicable)				X ^e

a. Clinical Variables form completed once at end of radiation treatment for every patient in monitoring phase

b. baseline questionnaires to be completed within ≤ 21 days prior to, or within 3 days of starting radiation therapy, otherwise they need to be repeated.

c. During final week of RT, and 4 weeks after completion of RT

d. LFTs, BUN/Creatinine, Hematocrit will be accepted if drawn within 30 previous day; TSH within 6 months.

e. To be completed by study coordinator at time when patient is taken off-study for any reason. If patient continues on to Intervention Phase, this form will be completed when taken off intervention phase.

**Study measures, type of procedure, and study visit schedule
Monitoring Phase (Partial Breast Irradiation (PBI))**

	Type	Baseline Visit	Monitoring Visits	Meets Fatigue Eligibility Threshold
Background Information				
Consent		X		
Demographics/Patient Characteristics Form	Self-report	X		
Clinical Variables ^a			X ^a	
Fatigue				
FACIT-Fatigue Subscale	Self-report	X ^b	X ^c	X
PGI-F	Self-report	X ^b		
Sleep				
PSQI	Self-report	X ^b		
ISI	Self-report	X ^b		
ESS	Self-report	X ^b		
Berlin Questionnaire	Self-report	X ^b		
Other Target Symptoms				
GAD7	Self-report	X ^b		
PHQ9	Self-report	X ^b	X ^d	
FACT-B/FACT-ES	Self-report	X ^b	X ^d	
CPFQ	Self-report	X ^b		
PEG	Self-report	X ^b		
Safety monitoring				
Urine β -HCG				X
LFTs ^e				X
BUN/Creatinine ^e				X
Hematocrit ^e				X
TSH ^e				X
Subject Exit form (if applicable)				X ^f

a. Clinical Variables form completed once at end of radiation treatment for every patient in monitoring phase

b. baseline questionnaires to be completed within ≤ 21 days prior to, or within 3 days of starting radiation therapy, otherwise they need to be repeated.

c. Complete once at baseline, once within one week after start of radiation, then once 4 weeks after completion of RT

d. Complete once at baseline, once within one week after start of radiation, then once while obtaining the final monitoring FACIT 4 weeks after end of RT

e. LFTs, BUN/Creatinine, Hematocrit will be accepted if drawn within 30 previous day; TSH within 6 months.

f. To be completed by study coordinator at time when patient is taken off-study for any reason. If patient continues on to Intervention Phase, this form will be completed when taken off intervention phase.

Study measures, type of procedure, and study visit schedule
Monitoring Phase (Hypofractionation Radiation)

	Type	Baseline Visit	Monitoring Visits	Meets Fatigue Eligibility Threshold
Background Information				
Consent		X		
Demographics/Patient Characteristics Form	Self-report	X		
Clinical Variables ^a			X ^a	
Fatigue				
FACIT-Fatigue Subscale	Self-report	X ^b	X ^c	X
PGI-F	Self-report	X ^b		
Sleep				
PSQI	Self-report	X ^b		
ISI	Self-report	X ^b		
ESS	Self-report	X ^b		
Berlin Questionnaire	Self-report	X ^b		
Other Target Symptoms				
GAD7	Self-report	X ^b		
PHQ9	Self-report	X ^b	X ^d	
FACT-B/FACT-ES	Self-report	X ^b	X ^d	
CPFQ	Self-report	X ^b		
PEG	Self-report	X ^b		
Safety monitoring				
Urine β -HCG				X
LFTs ^e				X
BUN/Creatinine ^e				X
Hematocrit ^e				X
TSH ^e				X
Subject Exit form (if applicable)				X ^f

a. Clinical Variables form completed once at end of radiation treatment for every patient in monitoring phase

b. baseline questionnaires to be completed within ≤ 21 days prior to, or within 3 days of starting radiation therapy, otherwise they need to be repeated.

c. Complete once at baseline, weekly during RT, then once 4 weeks after completion of RT

d. Complete once at baseline, once during the final week of RT, then once while obtaining the final monitoring FACIT 4 weeks after end of treatment

e. LFTs, BUN/Creatinine, Hematocrit will be accepted if drawn within 30 previous day; TSH within 6 months.

f. To be completed by study coordinator at time when patient is taken off-study for any reason. If patient continues on to Intervention Phase, this form will be completed when taken off intervention phase.

Study measures, type of procedure, and study visit schedule
Intervention Phase

	Week 0 Randomi zation Visit	Week 1 Rx Visit (+/- 7 days)	Week 5 Rx Visit (+/- 7 days)	Week 9 Follow- up Visit (+/- 7 days)
Background Information				
Consent	X			
Fatigue				
FACIT-Fatigue Subscale	X	X	X	X
PGI-I	X		X	
Sleep				
PSQI	X		X	
ISI	X		X	
ESS	X		X	
Berlin Questionnaire			X	
Other Target Symptoms				
GAD7	X		X	
PHQ9	X		X	
FACT-B/FACT-ES	X		X	
CPFQ	X		X	
PEG	X		X	
Safety monitoring				
LFTs			X	
Concomitant medications	X	X	X	
Adverse Events assessment		X	X	
Health status/life events review				X
Dispense medication	X	X		
Review medication diary	X	X	X	
Study Summary				
Subject Exit form				X ^a
Study Visit duration (min)	40	15	40	15

a. To be completed by study coordinator at time when patient is taken off-study for any reason.

Effect measures listed in the Table of Procedures are described below. In addition to these effect measures, we will examine potential covariates that may play a role in the evolution of fatigue during breast radiotherapy. These include radiotherapy related characteristics such as breast volume; type of radiotherapy (e.g. fractionation schedule, number of fields, design of tangent fields [e.g. partial vs. full breast irradiation], boost dose [mini-tangents vs. electrons]. Exercise type/frequency and travel time to clinic will be assessed, as these parameters have correlated with radiotherapy-emergent fatigue in prior studies³⁹. Finally, hematocrit will be measured at baseline.

The related symptom measure of obstructive sleep apnea will be evaluated via the Berlin Questionnaire and Epworth Sleepiness Scale:

Berlin Questionnaire (BQ): (Time: 2 minutes) The BQ will be done once at the beginning of the

study. It is an instrument used to identify patients at high risk for sleep apnea based on symptoms related to snoring and daytime sleepiness along with the presence of hypertension or obesity. It has been found to have high sensitivity and specificity in a primary care setting.⁴⁰

Epworth Sleepiness Scale (ESS): (Time: 2 minutes) The ESS is a simple self-report scale of sleep propensity. The subject is asked to estimate the chances of dozing in each of 8 different situations on a scale of 0 to 3, with total scores ranging from 0 to 24. The ESS has been validated as a tool to differentiate normal subjects from those diagnosed with a sleep disorder.⁴¹

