1.3 Secondary Objectives

1.3.1. To determine the effect of naltrexone on exploratory outcomes including: mood, anxiety, subjective cognitive function, sleep, pain, and quality of life, and the extent to which changes in fatigue correlate with changes in these symptom endpoints. These outcomes have been shown to be associated with cancer fatigue in prior studies involving breast cancer patients^{1 2-4}.

1.3.2. To determine the course, predictors, and correlates of fatigue during radiotherapy for breast cancer in a large controlled sample

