radiation-related fatigue in cancer patient populations who are not expected to require opioid therapy. Breast cancer patients receiving radiotherapy represent an important population to study because fatigue develops commonly during radiotherapy and concurrent therapy with opioids is rare. Notably, existing literature provides widely variable estimates (38-75%) of the prevalence of breast radiotherapy-emergent fatigue^{11,12} as well as differing evidence as to the most important predictors of fatigue in this population. Longitudinal studies have found that fatigue levels gradually increase during a course of breast radiotherapy, particularly during the first four weeks of treatment.¹³⁻¹⁵ Several studies have investigated clinical correlates of radiation-related fatigue in this population. Donovan found that patients (N=134) pre-treated with chemotherapy reported less fatigue during radiotherapy as compared to patients who did not receive chemotherapy, and that demographic and disease-related variables did not predict the extent of fatigue; however, psychological variables were not examined in this study.¹⁶ Manir described anemia as the most important predictor of fatigue (N=72)¹² whereas other studies have found no relationship between hemoglobin levels and fatigue.¹³ Recently, Taunk compared different radiotherapeutic regimens for early-stage breast cancer (overall N=80) and suggested that partial breast irradiation may reduce fatigue as compared to hypofractionated and standard whole breast irradiation.¹⁷ However, in the largest cohort study to date (N=250), Reidunsdatter identified medical comorbidity as a more important determinant of increased fatigue during breast radiotherapy than radiotherapy type.¹⁸ By contrast, Courtier reported that anxiety, elevated pre-treatment fatigue, and diagnoses other than invasive ductal carcinoma (e.g. DCIS or lobular subtypes) predicted radiation-emergent fatigue (N=100).¹¹ More study of the clinical correlates and course of fatigue during radiotherapy is warranted in the breast cancer population given the relatively small sample sizes, variable inclusion of relevant medical and psychosocial variables in models to predict fatigue, and conflicting findings to date. The monitoring phase of the present study offers an embedded opportunity to analyze the course, predictors, and correlates of radiotherapy-related fatigue in a controlled breast cancer population.

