5.3 Agent Administration

All participants will be instructed to swallow the double-blinded medications in the morning with food.

Monitoring and Intervention Phases: Visit Breakdown – Refer to study calendar in section 9.

Monitoring Phase (duration: 1-10 weeks):

- Visit 1: Collection of baseline data.
 - a. Patient demographic information and clinical characteristics will be collected by self-administered surveys.

- b. Completion of self-reported fatigue, anxiety, depression, sleep and quality of life questionnaires.
- Visits 2-10 (in person or by phone): Monitoring procedures including completion of self-reported fatigue and other quality of life questionnaires

The occasional mis-timed (or missed) FACIT does not automatically constitute a protocol violation. However, in order to remain in compliance with the protocol, a minimum of 4 FACITs is needed for partial breast irradiation patients, 5 FACITs for hypofractionation patients, and 7 FACITs for standard (6 week) fractionation patients. The monitoring phase terminates either at entrance into the intervention phase of the study, or at 4 weeks after the conclusion of radiation therapy, whichever comes first.

Intervention Phase (duration 5 weeks):

- Visit 1a:
 - a. consent for trial;
 - b. review of concomitant medications;
 - c. complete baseline fatigue questionnaire (unless completed within past week)—may be completed at Visit 1b;
 - d. complete anxiety, depression, sleep and quality of life questionnaires (unless completed within past week)—may be completed at Visit 1b;
 - e. urine HCG only in women with reproductive potential; blood draw to evaluate LFTs, Hct, BUN/Cr unless results are available within the previous month;
 - f. specimens will be banked for future analysis of fatigue-related genetic polymorphisms and inflammatory biomarkers (participants can opt out of specimen banking)
- Visit 1b: laboratory study results reviewed to confirm eligibility; receive medication bottles and medication diary; receive patient education sheet on contraindicated medications and safety card (see Appendix A); Visit 2 (one week after starting study drug vs. placebo): fatigue/response and adverse event assessment for dose escalation, review of concomitant medications, fatigue assessment

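### Hematocrit is named as a covariate for fatigue during radiotherapy but scheduled only for patients who have met the fatigue threshold, so it cannot be tested as a predictor of fatigue onset

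*Combined protocol and SAP*

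**What the plan says.** After the calendars in Section 9, the protocol states that "we will examine potential covariates that may play a role in the evolution of fatigue during breast radiotherapy". It names radiotherapy characteristics, exercise and travel time, and ends: "Finally, hematocrit will be measured at baseline". It does not say which phase's baseline is meant.

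The objective these covariates serve is 1.3.2: "To determine the course, predictors, and correlates of fatigue during radiotherapy for breast cancer in a large controlled sample". Section 2.1 places that work in the monitoring cohort: "The monitoring phase of the present study offers an embedded opportunity to analyze the course, predictors, and correlates of radiotherapy-related fatigue". The same section reports mixed evidence on anemia. One study "described anemia as the most important predictor of fatigue", while others found no link between hemoglobin and fatigue.

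The schedule is narrower. Each of the three monitoring calendars (six-week, partial breast, hypofractionated) lists hematocrit among the safety laboratory rows. It is marked only in the column for patients who reach the fatigue threshold, not at the baseline visit or the monitoring visits. A footnote adds: "LFTs, BUN/Creatinine, Hematocrit will be accepted if drawn within 30 previous day; TSH within 6 months". Section 5.3 describes the first monitoring visit as surveys and questionnaires. Blood appears at intervention Visit 1a, after consent to the trial: "blood draw to evaluate LFTs, Hct, BUN/Cr unless results are available within the previous month". The intervention calendar has no hematocrit row.

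**The concern.** To test whether a factor predicts who becomes fatigued, it must be known both for patients who become fatigued and for those who do not, and preferably before fatigue starts. Here, whether hematocrit is recorded depends on the outcome itself. Every patient with a scheduled value is already a case, and the value is taken at or near the time fatigue was detected.

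At stake is one candidate predictor on which the protocol's own background says the evidence conflicts. The monitoring cohort could add evidence on it, but the present schedule does not supply the data. The gap looks unintended. The other covariates named in the same paragraph have a collection route for all monitored patients. Hematocrit is also absent from the laboratory eligibility limits (Section 3.3.3) and from the removal criteria (Section 5.7), so the covariate paragraph gives its only stated analytic use.

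**Working it through.** The plan gives no figure of its own on this point, so the check compares the texts and then sizes the gap.

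**Step 1. Who has each covariate.**

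| Covariate in Section 9 | Where it is collected | Who has it |
|---|---|---|
| Radiotherapy characteristics | Clinical Variables form (footnote a to the monitoring calendars) | Every monitored patient |
| Exercise, travel time | Demographics form at the baseline visit | Every monitored patient |
| Hematocrit | Threshold column of the calendars; intervention Visit 1a in Section 5.3 | Only patients who meet the threshold |

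Under Section 5.3 the draw follows consent to the intervention, so a fatigued patient who declines may lack a value too.

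**Step 2. What can be estimated.** Let Y = 1 if a patient meets the threshold (a fall of at least 10 points on FACIT-F, Section 3.3.7). Scheduled hematocrit is observed only when Y = 1, so among patients with a value P(Y = 1) = 1 at every hematocrit level. No odds ratio or risk difference for onset can be formed. Replacing Y with the continuous change in FACIT-F does not restore the comparison, because everyone with a value has fallen by at least 10 points. The protocol specifies no model for 1.3.2. Imputation would not help either, since no observed hematocrit exists among non-cases to inform it.

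**Step 3. Timing among cases.** The 30-day allowance mixes periods. On a six-week course (42 days), a patient who meets the threshold on day 14 could supply a value from up to 30 − 14 = 16 days before radiotherapy. A patient who meets it on day 42 could supply nothing earlier than day 42 − 30 = 12 of treatment.

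**Step 4. Illustrative size.** Inputs from Section 12.2: about 225 screened per year, 4 years, 30% fatigue rate. From Section 2.1: prevalence of 38-75%.

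- Monitored: 225 × 4 = 900.
- At 30%: 900 × 0.30 = 270 with a value; 900 − 270 = 630 (70%) without.
- At 38%: 342 with; 558 (62%) without.
- At 75%: 675 with; 225 (25%) without.

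Section 12.2 says the monitoring sample size is not fixed. Its inputs also do not quite fit together: 270 cases is below the 300 to be randomized (150 per arm), which at 30% would need 300 / 0.30 = 1,000 monitored, with 700 lacking a value. The 70% share is the same either way. In every row, all patients below the threshold lack a value.

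**The case against.** The strongest reply is that baseline may mean the intervention baseline. Section 5.3 uses the word that way for the fatigue questionnaire at Visit 1a, where hematocrit is also drawn, and the sentence in question comes just after the intervention calendar. On that reading the texts do not contradict each other. This stands as a point about wording. It does not close the gap, because the covariates are offered to explain how fatigue evolves during radiotherapy, and Section 2.1 assigns that question to the monitoring phase.

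Second, a reader might infer that hematocrit is useless for objective 1.3.2. The documents do not support that. The objective covers course and correlates as well as predictors, and hematocrit could still be related to severity or later course among patients who met the threshold. Only the onset comparison is lost.

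Third, a reader might infer that the monitoring cohort exists to settle the anemia question. Section 2.1 does not say so. Anemia is one of several disputed predictors, alongside prior chemotherapy, radiotherapy regimen, comorbidity, anxiety, pre-treatment fatigue and histology, and objective 1.3.2 names none of them.

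Fourth, every monitored patient is asked about anemia on the demographics form, once as a lifetime condition and once as a possible cause of fatigue before breast cancer. Both are self-reported history, not current hematocrit. Routine blood counts may exist in the medical record, but the plan does not say it will collect them for patients below the threshold.

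**Conclusion.** The concern holds for fatigue onset. As scheduled, all monitored patients who stay below the threshold lack a protocol-collected hematocrit, so it cannot be tested as a predictor of onset in the monitoring cohort. This rests on the calendars and Section 5.3 being followed as written, and it holds under either meaning of baseline.

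The counts are illustrative. About 630 of 900 without a value should not be read as a firm figure: it is the upper end of a range of 225 to 630 across the fatigue rates the protocol quotes, on a sample size it leaves open. The conclusion does not depend on them.

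The matter is worth correcting but limited. It affects one candidate covariate in a secondary objective and leaves the primary endpoint, randomization and intervention sample size untouched.

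**What to change.** Reconcile the covariate paragraph in Section 9 with the calendars:

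- For every monitored patient, have the study coordinator abstract the most recent clinical hematocrit before the first radiotherapy fraction, with its date and within a stated look-back window.
- Put this on a coordinator-completed baseline field. The Clinical Variables form is a poor place for it, because it is completed at the end of radiation and Section 10.1 assigns it to a dosimetrist or physicist.
- Mark hematocrit in the baseline column of all three monitoring calendars, and name this value as the predictor for 1.3.2. Keep the draw at the threshold for its present purpose.
- Report missing hematocrit by prior chemotherapy and adjust for chemotherapy in the analysis. I assume that having a recent blood count depends partly on prior chemotherapy, which one study cited in Section 2.1 linked to fatigue. The forms reproduced in the protocol mention chemotherapy only in the menopause questions, so the coordinator should record it for every monitored patient as well.

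The cost is a short chart abstraction per patient and a calendar edit, with no new blood draw. Section 4.1 describes record review for identifying patients, so the team should confirm that the monitoring consent covers abstracting a laboratory value. Some values will still be missing.

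If abstraction is not done, Section 9 should limit the stated use of hematocrit to the intervention group. That costs nothing but gives up the onset question.
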